#### **14.0 PATHOLOGY GUIDELINES AND SPECIMEN REQUIREMENTS**

Before entering patients on this trial, clinicians should discuss this protocol with their pathologist and provide them with pathology section of the protocol and list of the required materials that will need to be submitted. (Requirements are listed on the Data Submission Schedule in the CRF packet.)

It is the responsibility of the Principal Investigator at the institution to ensure that the pathologist is informed of each patient enrolled on AHEP0731 and to request that patients' materials be forwarded to the COG Biopathology Center (BPC), as required. The BPC will NOT request materials.

#### 14.1 Pathology Evaluation

The pathologic classification of liver tumors is becoming increasingly complex. Because of limited biopsy specimens for review, the diagnosis of hepatoblastoma is sometimes difficult to make. Central review is therefore critical to ensuring that the diagnosis is accurate and that patients are treated appropriately. Central pathologic review will be performed on all diagnostic specimens (whether resected or biopsied). Results of the review will only be given to the treating institution for Stage I and II patients who receive rapid central pathology review.

If there is a discrepancy between the institutional diagnosis and the diagnosis on the central review of a Stage I or II patient, then a discussion between the local and study pathologists will take place to attempt to reach a consensus. If a consensus cannot be reached, then the institutional diagnosis will be accepted. An assessment of the influence of the exclusion of cases for whom there is a discrepancy in diagnosis between institutional and central review, or for whom there is an exceptional or unusual histological presentation will be addressed statistically.

Please label all materials with the patient's COG Patient Identification Number and the surgical pathology number and block number from the corresponding institutional pathology report(s).

There are 2 study pathologists: Drs. [name] and [name].

There are 2 JPLT study pathologists: Drs. [name] and [name].

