#### 2.3.4 High-Risk Patients

High-risk patients include: 1) any patient with metastatic disease; 2) any patient with a low diagnostic AFP level < 100 ng/mL, regardless of stage (see [Section 7.1](#)).

Based on multiple cooperative group studies, the 40-70% EFS for unresectable patients and 20-40% EFS for metastatic patients remain suboptimal (see Table 2). The optimal dose of cisplatin to administer to patients with unresectable and metastatic disease is unclear. However, as cisplatin is the most active agent for hepatoblastoma, intensification of cisplatin therapy may be beneficial. The dose of cisplatin proposed for intermediate- and high-risk patients in this trial exceeds doses used in other trials. SIOPEL administers an additional 3 grams of platin-based therapy with carboplatin to patients who receive 320 mg/m^2 of cisplatin. SIOPEL-4, the current study for high-risk patients includes cisplatin (570 mg/m^2), doxorubicin (300-350 mg/m^2) and 2-3 courses of carboplatin. The HB studies administer 12,000 mg/m^2 of ifosfamide. Table 3 provides a dose comparison of the cumulative chemotherapy dosing for intermediate- and high-risk patients being used in current studies.

Table 3. Cumulative Dosage\* of Chemotherapy in Advanced-Stage Patients According to Treatment Regimen

Study	CDDP	DOXO	IFOS	CARBO	VCR	FU
AHEP0731	600	360	0	0	33-39	3600
P9645	600	0	0	0	0	0
SIOPEL-2	320	360	0	3000	0	0
SIOPEL-4	570	300-350	0	2-3 courses	0	0
HB-GPOH	400	240	12000	0	0	0

\*Chemotherapy dosing is mg/m^2

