#### 2.4 Prognostic Variables

The decline of AFP levels after 4 cycles of chemotherapy and prior to surgical resection of the tumor has been shown to have prognostic value. However, no data have been reported to suggest that the initial rate of decline or the magnitude of decline of AFP after each cycle can be used to guide therapy. Data analyzed from INT-0098 and P9645 do not support AFP decline as a useful tool in low-risk patients (personal communication, Dr. [name]). Initial AFP < 100 ng/mL has been described as being associated with an adverse outcome. While older reports of liver tumors with low AFP levels may include some misdiagnoses with other malignant liver disorders, recent reports continue to suggest that AFP < 100 ng/mL is associated with worse prognosis in hepatoblastoma. Data from SIOPEL evidenced 3-year EFS of 13% in patients with a low AFP regardless of stage. As a result, patients in AHEP0731 with a low AFP at the time of initial diagnosis regardless of stage will be considered to be high-risk and treated accordingly (see [Section 7.1](#)).

Additional risk factors including histologic subtype, especially macrotrabecular and small cell undifferentiated, PRETEXT group, surgical margin, surgical complications, and diffuse multifocal tumors have been reported to have potential prognostic value in hepatoblastoma and should be further investigated in a prospective, multigroup setting. Collaboration among international colleagues would be particularly advantageous for the collection of these potential prognostic variables, thereby enabling the data to be pooled into a cooperative database and allowing increased statistical power to make subtle, or rare, observations.

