#### 3.1.5 Timing

All patients must be enrolled on AHEP0731 before protocol treatment begins. The date protocol therapy is projected to start must be no later than 42 days (28 days preferred) from biopsy or definitive surgery, whichever occurs latest, except in the case AHEP0731 therapy is started in an emergent situation (see [Section 3.2.2.b](#) below). **Investigators are strongly encouraged to enroll patients immediately following histological diagnosis and begin protocol therapy within 28 days of the initial surgical procedure.**

**Patients with Stage I and II tumors (see [Appendix III](#)) require rapid central pathologic review and enrollment of these patients on AHEP0731 must not occur until the results of rapid central pathologic review are known. Stage I and II tumor specimens are to be submitted immediately following histological diagnosis. Pathology specimens MUST be submitted no later than 14 calendar days (7 days preferred) from definitive surgery and be accompanied by a Rapid Review Transmittal Form found on the AHEP0731 protocol page of the COG website. If Stage I and II diagnostic specimens are not submitted within 14 days of initial surgery, the patient will **not** be eligible for this study. **Enrollment of Stage I and II patients onto this study must not occur until the results of rapid central pathologic review are known and these results must be provided by the institutional investigator on the AHEP0731 Eligibility CRF.****

Retrospective central pathologic review is also required for all other biopsied/resected specimens (liver and/or lung). Specimens must be submitted within 4 weeks from all biopsies/resections other than Stage I and II diagnostic procedures. These specimens will be submitted using the generic COG Specimen Transmittal form. See [Section 14.1.1](#) for details.

**All clinical and laboratory studies to determine eligibility must be performed within 14 days prior to enrollment unless otherwise indicated in the eligibility section below.**

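### Section 14.1 gives a central reading of a diagnosis other than hepatoblastoma no route to the treating site for a biopsied Stage III/IV child

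*Combined protocol and SAP*

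**What the plan says.** Section 14.1 explains that limited biopsy material sometimes makes hepatoblastoma hard to diagnose. It continues: "Central review is therefore critical to ensuring that the diagnosis is accurate and that patients are treated appropriately". Review covers all diagnostic specimens, resected or biopsied.

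The return of results is narrower: "Results of the review will only be given to the treating institution for Stage I and II patients who receive rapid central pathology review". The discussion between local and study pathologists is triggered only by disagreement with the "diagnosis on the central review of a Stage I or II patient". Where that discussion takes place, the site keeps the last word: "If a consensus cannot be reached, then the institutional diagnosis will be accepted".

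Stage III and IV diagnostic biopsies fall under the other tier in Section 3.1.5: "Retrospective central pathologic review is also required for all other biopsied/resected specimens (liver and/or lung". On timing, the same section says "Specimens must be submitted within 4 weeks from all biopsies/resections other than Stage I and II diagnostic procedures". No date is set for the reading itself.

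Sections 9.2 and 14.1 plan a statistical look at the influence of cases where the institutional and central diagnoses differ.

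**The concern.** The stated reason for central review is that small biopsies can mislead. The children with small biopsies are mostly Stage III and IV, because Section 13.1.1b directs biopsy only for the larger tumors. Stage I and II are resected tumors (Appendix III). The children whose limited tissue justifies the review are thus the ones whose sites do not receive the result.

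The gap matters only for the diagnosis itself. Subtype assigns treatment in Stage I and II before enrollment, so rapid return there makes sense. In Stage III and IV the regimen does not depend on subtype, and a retrospective reading is enough. A reading that the tumor is a different disease is another matter. Such a child could go on to 600 mg/m² of cisplatin and 360 mg/m² of doxorubicin (Table 3), and possibly to liver transplant, while the study holds a contrary diagnosis that it plans to use only in a summary comparison.

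**Working it through.** The plan gives no figure to reproduce. The check is mainly textual, followed by date arithmetic to judge size.

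**Is there another route to the site?** Each place that could supply one was compared with 14.1:

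- Section 14.1.1: the named recipient of results is the contact on the Stage I/II rapid-review form.
- Section 9.2: review results are returned to the investigator for Stage I and II only.
- Sections 4.1, 4.6, 10.3 and 15.3: the central review returned for Stratum 4 covers imaging and AFP response, not histology.
- Sections 3.2.2.b, 8.2(f) and 9.2: contrary later pathology is acted on for children enrolled without a biopsy. A biopsied child is not covered.
- Section 8.1: no removal criterion refers to central diagnosis. Criterion (j), physician judgment, presupposes that the physician knows the result.

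No exception was found.

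**Could a reading fall within treatment?** Slides are due 28 days after biopsy, and therapy starts 0 to 42 days after biopsy (3.1.5). Slides are therefore due between 14 days before Day 1 (28 − 42) and Day 28 of treatment. Non-responder chemotherapy lasts 8 × 21 = 168 days and responder chemotherapy 10 × 21 = 210 days. Section 4.6 intends removal of the primary at the latest after Cycle 6, which is 6 × 21 = 126 days. In the least favorable case, 126 − 28 = 98 days remain before that point when slides are due. A reading in time is possible, although no rule requires one.

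**Who could still be affected at this version?**

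- Stratum 3 closed on 03/12/12, so its six cycles are long finished. What remains is Stratum 4: Stage IV, and Stage III children who enter it under "any patient with a low diagnostic AFP level < 100 ng/mL, regardless of stage".
- Accrual closed on July 20, 2018 and this version is dated November 7, 2018: 11 + 31 + 30 + 31 + 7 = 110 days.
- Resection gives the site its own larger specimen, so the useful period is mainly before day 126. November 7 minus 126 days is July 4. Children who started before July 4 were past that point.
- Enrollment window: 126 − 110 = 16 days if therapy starts at enrollment, or 16 + 42 = 58 days if it starts 42 days later, the limit used in 9.2.

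Two accrual assumptions:

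- The planned 16 per year (9.1) continuing to closure: 16/365.25 × 16 = 0.7 and 16/365.25 × 58 = 2.5 children.
- The target of 43 (9.2) spread from 03/12/12 to July 20, 2018, about 6.4 years: 43/6.4 ≈ 6.8 per year (43/6.36 before rounding the years), giving 6.8/365.25 × 16 = 0.3 and 6.8/365.25 × 58 = 1.1 children. The start date is an assumption, because the documents do not date Amendment 3B.

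If Stratum 4 filled before mid-2018, the count is 0. At the planned rate it would fill in 43/16 = 2.7 years. The range is therefore about 0 to 2.5. Delayed surgery, or the Cycle 7 point that 13.1.5 uses for transplant or extreme resection in responders, would add up to 16/365.25 × 21 = 0.9 child per extra cycle at the planned rate.

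These are children at risk of a missed message, not misdiagnosed children. The expected number affected is this count times an unknown discordance rate. At 2.5 children, the rate would have to be 1/2.5 = 40% for the expectation to reach one.

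Slides from biopsies done by July 20, 2018 were due by August 17, 2018, so some readings may already be on file.

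**The case against.** The two tiers look deliberate. Histology decides Stage I/II treatment, so that review is rapid and returned. For other specimens, Section 14.1.1 gives the aims as margins, satellite nodules and venous invasion, which overlap the prognostic factors in aim 1.3.8. Nothing says that Stage III/IV slides are read during treatment, resection gives a local check, and a returned reading would not override the site. All of this stands and keeps the severity low. It does not remove the gap, because 14.1 itself states a diagnostic and treatment purpose and then rules out return.

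A reader might infer more than the documents support:

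- *That low-AFP children are known to be misdiagnosed on this trial.* Section 2.4 says "While older reports of liver tumors with low AFP levels may include some misdiagnoses with other malignant liver disorders", but this concedes a weakness of older reports, and the sentence goes on to say that recent reports still link low AFP with worse prognosis in hepatoblastoma. The elevated-AFP condition in 3.2.2.b keeps low-AFP children out of the no-biopsy route, which is a safeguard.
- *That the emergent-enrollment rules are a precedent.* They concern children with no initial histology and act on tissue from a later procedure. They do not return a central reading that contests an existing diagnosis.
- *That more children are exposed, counting to the end of chemotherapy.* At 16 per year with a 42-day lag, the responder window is 210 − 110 + 42 = 142 days, or 6.2 children. That rate up to closure fits poorly with a target of 43, and the count ignores the specimen obtained at resection.
- *That a plausible discordance rate can be applied.* The documents give none.
- *That an estimate or decision rule is wrong.* Nothing here shows that.

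**Conclusion.** The point holds as a narrow communication gap. Section 14.1 justifies central review by diagnostic accuracy in limited biopsies, yet it leaves a contrary diagnosis in a biopsied Stage III/IV child without a route to the treating site. This is a stated rule with no exception elsewhere, and not merely an omitted detail.

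Its practical size is small and cannot be computed from the documents. At this version it concerns at most a few late-enrolled Stratum 4 children: roughly 0 to 2.5 before the intended resection point, and possibly none. That range rests on uninterrupted 21-day cycles, resection by Cycle 6, and enrollment at 0, 6.8 or 16 per year up to closure. The change is optional but cheap, and worth making for patient safety.

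**What to change.** Add to 14.1: when central review of a Stage III or IV specimen gives a diagnosis other than hepatoblastoma, as opposed to an inconclusive or limited sample, the reading is sent when made to the treating institution and the study chair. It triggers the local-central pathologist discussion already described there. If there is no consensus, the institutional diagnosis stands. Any such reading already on file for a child still on protocol therapy is sent at once. Subtype results need not be returned. The text should also say whose reading counts, since 14.1 lists two study pathologists for COG and two for JPLT.

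The cost is one short addition, plus one message and one discussion per discordant case. No new review is needed, and Stratum 4 sites already receive a central imaging and AFP result within 3 weeks of submission (4.6). The limitation is that, without a reading deadline, slides read after treatment bring no benefit, and time taken to implement the change shortens the remaining window.

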##### 14.1.1 Central Pathology Review

Central pathologic review will be performed for all resected/biopsied specimens (liver and/or lung) to assess for the presence of positive surgical margins, microscopic satellite nodules, and microscopic venous invasion. Specimens should be submitted at the time of diagnosis and from all subsequent biopsies or resections or explants.

- **Stage I and II Specimens at Diagnosis**

Rapid central pathology review of all Stage I and II patient specimens is required. Rapid central pathology review was utilized on the P9645 study and was shown to be feasible. Two sets of duplicate slides of the entire specimen must be SUBMITTED to the COG Biopathology Center (BPC) no later than 14 calendar days from resection (7 days preferred). The BPC will immediately forward one set to one of the study pathologists. **Enrollment on this study of Stage I or II patients must not occur until results of rapid central pathologic review are known.** The study pathologists will review all slides and will communicate results to the contact person noted on the Rapid Review Transmittal Form for Stage I and II patients. If there is > 1 week delay from submission of specimens for rapid review and receipt of pathology review, the study chair should be contacted.

Required materials for Stage I and II are:

Paraffin-embedded blocks are preferred; if all blocks with tumor are not available, then send 2 H&E and 2 unstained slides per block.

- A **minimum** of 1 block of tissue for each 1 cm of maximum tumor diameter should be sampled
- **Sections of tumor should measure approximately 2.5 x 1.5 cm per paraffin block**
- Include the surgical margin (1 section for each cm of resection margin)
- Include the peri-or intra-hilar portal vein and hepatic vein at margin of resection

- Include any well-defined encapsulated circular foci of tumor suggestive of intravenous growth
- Representative sections of grossly diverse appearing areas (most closely resembling normal liver and moderately firm to capture 'fetal' histology; softer more pale, pinkish and moist areas for 'embryonal' or 'small cell' components; more firm and even calcified areas for fibrous and 'osteoid' mesodermal derivatives; dark brown foci for melanotic 'teratoid' elements). Some or all of these sections may also meet the requirement for marginal material. It is very desirable to photograph the gross specimen and to diagram {map} the precise source of the samples.

**Special Instructions:** It should be noted on the AHEP0731 Rapid Review Transmittal Form for Stage I and II patients that the specimen is for a Stage I or II rapid review at diagnosis.

- **All Other Specimens (all surgeries except initial Stage I and II surgery)**  
Histologic sections of all remaining pathology specimens will be sent to the BPC (see address below). Slides must be submitted following **all** other surgical biopsies/resections including:
  - Non-Stage I or II diagnostic biopsy
  - Primary upfront resection
  - Delayed surgical resection
  - Liver explant at time of orthotopic liver transplant
  - Pulmonary metastectomy

Slides must be submitted within **4 weeks** of surgical procedure. Required materials for all surgeries (except initial Stage I and II surgery) are:

Paraffin-embedded blocks are preferred; if all blocks with tumor are not available, then send 2 H&E and 2 unstained slides per block.

- **A minimum** of 1 block for each 1 cm of maximum tumor diameter
- **Sections of tumor should measure approximately 2.5 x 1.5 cm per paraffin block**
- Include the surgical margin (1 section for each cm of resection margin)
- Include the peri- or intra-hilar portal vein and hepatic vein at margin of resection
- Include any well-defined encapsulated circular foci of tumor suggestive of intravenous growth
- Representative sections of grossly diverse appearing areas (most closely resembling normal liver and moderately firm to capture 'fetal' histology; softer more pale, pinkish and moist areas for 'embryonal' or 'small cell' components; more firm and even calcified areas for fibrous and 'osteoid' mesodermal derivatives; dark brown foci for melanotic 'teratoid' elements). Some or all of these sections may also meet the requirement for marginal material. It is very desirable to photograph the gross specimen and to diagram {map} the precise source of the samples.

#### 14.1.2 Pathology Submission Requirements

All materials must be submitted with the following identification:

- COG Registration Number
- Surgical Pathology ID (SPID) Number
- Block Number

The following items from each surgical procedure must also be submitted:

Pathology Report

Pathology Checklist

Operative report

Specimen Transmittal Form (Stage I & II tumors use specific form for rapid review submission available on AHEP0731 protocol page on COG website; all other submissions use the COG Generic Specimen Transmittal form)

Any gross image with mapping if performed

## 14.2 **Biology Studies**

The submission of diverse tumor and corresponding normal tissue for biologic studies is strongly encouraged. Please submit biology specimens using ABTR01B1 or other appropriate study.

## 15.0 **IMAGING STUDIES REQUIRED AND GUIDELINES FOR OBTAINING**

### 15.1 **Primary Site Imaging**

The same modality used at baseline should be used for all follow-up imaging.

#### 15.1.1 Primary Site Computed Tomography

1. All CT scans should be done with technical factors using the lowest radiation exposure possible (ALARA principle) that allow optimal image quality.
2. CT slice *acquisition* thickness should be 1.5 mm or less.
3. Post-contrast IV enhanced portal venous phase abdominal and pelvic CT should be performed from just above the diaphragm to the symphysis pubis. Dual phase (arterial and portal venous) abdominal CT is strongly recommended.
4. Oral contrast is strongly recommended.

#### 15.1.2 Primary Site Magnetic Resonance Imaging

Axial images and coronal images of the liver tumor should be acquired with at least two pulse sequences, including T1 and either fat-suppressed T2, STIR, or fat-suppressed fast/turbo imaging. Gadolinium should be given if appropriate and if there is normal renal function. After contrast administration T1W, fat-suppressed, axial images should be obtained. Based on patient age, images may be non-breath-hold or breath-hold, including respiratory triggered or respiratory gated.

Dual phase MRI may be performed at the discretion of the local radiologist. To perform dual phase MR, gadolinium-enhanced imaging is performed in combination with dynamic gradient echo sequences. After

contrast agent injection, images are obtained through the liver during the arterial phase (20 to 30 seconds post injection), portal venous phase (60 to 80 seconds after injection), and at equilibrium (3 to 5 minutes after injection). Delayed images can be obtained if needed for further lesion characterization.

### 15.2 Metastatic Site Imaging

Chest CT is required to evaluate metastatic disease. Chest CT may be performed without intravenous contrast material. The diameter of a "measurable" nodule should be at least twice the reconstructed slice thickness. Smaller nodules are considered detectable, but will be counted as "non-measurable. Bone scan is not required but should be considered in symptomatic patients with bone pain or bone lesions. Metastatic disease to bone and bone marrow is extremely rare and should only be considered if the patient is symptomatic with unexplained bone pain or unexplained cytopenias.

